9.3.2 Reporting a Suspected Unexpected Serious Adverse Reaction (SUSAR)

All SAEs that are ‘suspected’ and ‘unexpected’ are to be reported to CRO Drug Safety Navigator within 24 hours after the site becomes aware of the event, via the SAE reporting process outlined above. All SAE/SUSARs will be promptly reported to the IRB/IEC and governing health authorities (e.g., United States Food and Drug Administration [FDA]) as required by the IRB/IEC, federal, state, and local regulations and timelines.

9.4 Procedures for Unmasking of IMP

All subjects, investigators, and trial personnel involved with the conduct of the trial will be masked with regard to treatment assignments. The mask may be broken in exceptional circumstances.

In a medical emergency, when the management of a subject’s condition requires knowledge of the treatment assignment, the investigator, or designee, will obtain the trial treatment assignment from the Interactive Response System (IRS). If possible, the medical emergency should be discussed with the medical monitor prior to obtaining the treatment assignment, or as soon after as possible. The sponsor may unmask for regulatory submission determination of an SAE when necessary (see [Section 0](#)).

In a non-emergency situation, when a code break is required, it must be discussed with the medical monitor and/or CRO Drug Safety Navigator and the trial sponsor. The code break must be approved in writing by the sponsor.

If the randomization code for a subject is broken, the investigator will record the date and reason for lifting the mask for that subject in the source documents. Upon unmasking, the subject will be withdrawn from the trial and should complete both the Early Termination and Follow-up procedures.

9.5 Type and Duration of the Follow-up of Subjects after Adverse Events

The investigator will follow unresolved AEs to resolution until the subject is lost to follow-up or until the AE is otherwise classified. Resolution means the subject has returned to baseline state of health or the investigator does not expect any further improvement or worsening of the AE. If the subject is lost to follow-up, the investigator should make 3 reasonable attempts to contact the subject via telephone, post, or certified mail. All follow-up will be documented in the subject’s source document. Non-serious AEs identified on the last scheduled contact must be recorded on the AE eCRF with the status noted.

If the investigator becomes aware of any new information regarding an existing SAE (i.e. resolution, change in condition, or new treatment), a new SAE Report Form must be completed and faxed to CRO Drug Safety Navigator within 24 hours of the site's awareness of the new information. The original SAE form is not to be altered, but a new SAE Report Form must be completed and identified consecutively based on the previous report form (i.e. Initial Report, Follow-up #1, Follow-up #2, etc.). The report must describe whether the event has resolved or continues and how the event was treated.

9.6 Reporting Pregnancies

Pregnancy itself is not considered an AE or SAE (unless there is a suspicion that the IMP may have interfered with the effectiveness of a contraceptive medication). Pregnancy is an important medical event that must be followed up. Any pregnancy that occurs during the clinical trial where the fetus could have been exposed to IMP must be followed through the outcome of the pregnancy.

It is the responsibility of the Investigator to obtain the outcome and information of the fetus or infant within approximately 30 calendar days postpartum.

If a subject or investigator suspects that the subject may be pregnant prior to IMP administration, the IMP must be withheld until the results of pregnancy testing are available. If pregnancy is confirmed, the subject must not receive IMP and must not be enrolled in the trial. If pregnancy is suspected while the subject is receiving IMP treatment, the IMP must immediately be withheld until the result of pregnancy testing is known.

If a female reports a pregnancy or has a positive pregnancy test during the trial, then the investigator must report the pregnancy and the outcome of the pregnancy to the CRO Drug Safety [REDACTED] Associate within 24 hours of learning about the pregnancy and outcome of the pregnancy respectively.

A Pregnancy Report Form will be completed by the trial site's principal investigator and sent to CRO Drug Safety [REDACTED] The CRO Drug Safety Navigator will forward the documentation to the medical monitor and the sponsor for review.

At the completion of the pregnancy, the Pregnancy Report Form is to be submitted to the CRO Drug Safety Navigator via the SAE contact details. The CRO Drug Safety [REDACTED] will manage the query and reconciliation process until the pregnancy documentation is complete.

10 STATISTICAL HYPOTHESES AND METHODS OF ANALYSES

10.1 Analysis Populations

The following analysis populations will be considered:

Full Analysis Set (FAS) – The FAS includes all randomized subjects who received at least one dose of investigational product. The primary analysis will be performed on the FAS. Subjects in the FAS will be analyzed as randomized.

Per Protocol Set (PPS) – The PPS includes subjects in the FAS who do not have significant protocol deviations and who complete the study. Protocol deviations will be assessed prior to database lock and unmasking. The PPS will be analyzed using observed data only for efficacy variables. Subjects in the PPS will be analyzed as treated.

Safety Set (SAF) – The SAF includes all randomized subjects who have received at least one dose of the investigational product. The SAF will be analyzed for all safety assessments. Subjects in the SAF will be analyzed as treated.

The statistical analysis of safety data will be performed for the SAF. The analysis of baseline and efficacy data will be performed for the FAS. The primary efficacy analyses will also be performed on the PPS as sensitivity analyses.

10.2 Statistical Hypotheses

The primary endpoints will be tested in a hierarchical fixed sequence in the following order.

The statistical hypotheses for the primary endpoint of CFB corneal fluorescein staining (NEI scale) total score at Day 57 are as follows:

H_{01} : The difference, between study eyes treated with NOV03 and study eyes treated with saline, in the mean CFB corneal fluorescein staining (NEI scale) total score at Day 57 = 0.

H_{A1} : The difference, between study eyes treated with NOV03 and study eyes treated with saline, in the mean CFB corneal fluorescein staining (NEI scale) total score at Day 57 $\neq 0$, with superiority claimed if the difference is less than 0 (NOV03 minus saline).

The statistical hypotheses for the hierarchical primary endpoint of the CFB Dryness Score at Day 57 are as follows:

H_{02} : The difference, between subjects treated with NOV03 and subjects treated with saline, in the mean CFB Dryness Score at Day 57 = 0.

H_{A2} : The difference, between subjects treated with NOV03 and subjects treated

with saline, in the mean CFB Dryness Score at Day 57 $\neq 0$, with superiority claimed if the difference is less than 0 (NOV03 minus saline).

Hierarchical fixed sequence testing will be employed to maintain the type I error rate within the two primary endpoints. The primary analyses will first test the difference in the mean CFB corneal fluorescein staining (NEI scale) total score between treatments at Day 57. If the test of the difference is statistically significant at the two-sided alpha = 0.05 level in favor of NOV03 then the trial will be considered a success; NOV03 will be declared to be superior to saline in the mean CFB corneal fluorescein staining (NEI scale) total score at Day 57; and the difference in the mean CFB total Dryness Score between treatments at Day 57 will be tested at the two-sided alpha = 0.05 level.

If in addition to a statistically significant test of the difference in the mean CFB corneal fluorescein staining (NEI scale) total score at Day 57 is in favor of NOV03, and the test of the difference in the mean change from Dryness Score at Day 57 is also statistically significant in favor of NOV03, then NOV03 will be declared to be superior to saline in both the mean CFB corneal fluorescein staining (NEI scale) total score and the mean CFB of the Dryness Score at Day 57.

10.3 Sample Size

The study has been designed to have at least 95% power to reject both H_{01} and H_{02} assuming independence between the sign and symptom endpoint; positive correlation between these two endpoints would increase the overall power.

Two hundred fifty (250) subjects (study eyes) per treatment group yields 97.9% power to reject H_{01} in favor of H_{A1} and conclude superiority of NOV03 over saline in the mean CFB tCFS score at Day 57 assuming a true difference (NOV03 minus saline) of -1.0, a common standard deviation of 2.8, and a two-sided alpha = 0.05. Two hundred fifty (250) subjects per treatment group yields 97.9% power to reject H_{02} in favor of H_{A2} and conclude superiority of NOV03 over saline in the mean CFB Dryness Score (VAS) at Day 57 assuming a true difference (NOV03 minus saline) of -10, a common standard deviation of 28, and a two-sided alpha = 0.05. Accounting for an assumed 10% subject discontinuation rate, approximately 560 subjects (280 subject each arm) will be randomly assigned to trial treatment such that approximately 250 evaluable participants per arm complete the trial.

Therefore, assuming independence between tCFS score and Dryness Score (VAS), 250 FAS subjects per treatment group at Day 57 yields $97.9\% * 97.9\% = 95.8\%$ power to reject both H_01 and H_02 .

10.4 Statistical Analysis

10.4.1 General Considerations

Quantitative variables will be summarized using number of subjects (n), mean, median, standard deviation, minimum and maximum. The qualitative variables will be summarized using counts and percentages.

All summaries will be presented by treatment group. Summaries will be provided for demographics, baseline medical history, concurrent therapies, and subject disposition.

For the purpose of summarization, medical history, concurrent therapies, and AEs will be coded to MedDRA and WHO Drug dictionaries, as appropriate.

Baseline measures are defined as the last non-missing measure prior to the initiation of randomized study treatment.

All primary and secondary analyses will be two-sided at a significance level of 0.05.

10.4.2 Unit of Analysis

For efficacy endpoints, the unit of analysis will be the study eye as defined by the following:
Study Eye: Eyes are eligible for analysis if they meet all of the inclusion criteria. In the case that both eyes are eligible for analysis, the worst eye shall be chosen, and this will be defined as the eye with worse (higher) total corneal staining at Visit 1. If the total corneal staining is the same in both eyes then the right eye will be selected as the study eye.

10.4.3 Missing Data

The primary analysis will be completed on the FAS with available data per subject, assuming the overall study discontinuation rate is $<5\%$. If the overall study discontinuation rate is $\geq 5\%$ then the primary analysis will be based on the primary imputation methodology as defined [Section 10.4.5](#) and the available data analyses will become robustness analyses.

Additionally, robustness analyses will include repeating the primary analysis on the per protocol set (PPS); the FAS imputing missing data using last observation carried forward (LOCF); the FAS imputing missing data using Markov Chain Monte Carlo (MCMC) multiple imputation methodology under different assumptions of missingness (at random and not at random) each using 30 imputed values.

The imputation model, for each visit, under the assumption of missing **at random** is:

```
PROC MI DATA=INDATA SEED=50048 OUT=OUTDATA1 MINIMUM = 0 MAXIMUM = 3 ROUND  
= 1 NIMPUTE=30;  
  MCMC INITIAL=EM;  
  BY <TREATMENT>;
```

```
VAR <BASELINE> <PARAMETER>;
RUN;
where PARAMETER has 5 levels and refers to the corneal fluorescein staining
score for each region (inferior, superior, central, temporal, and nasal).
The imputation model, for each visit, under the assumption of missing not at
random is:
PROC MI DATA=INDATA SEED=35852 OUT=MDATA MINIMUM = 0 MAXIMUM = 3 ROUND =
1 NIMPUTE=30;
  MCMC IMPUTE=MONOTONE;
  VAR <BASELINE> <PARAMETER>;
RUN;

PROC MI DATA=MDATA SEED=48778 OUT=OUTDATA2 MINIMUM = . 0 0
  MAXIMUM = . 3 3 ROUND = . 1 1;
  CLASS <TREATMENT>;
  MONOTONE REG(<PARAMETER> = <BASELINE> / DETAILS);
  MNAR MODEL(<PARAMETER> / MODELOBS=(<TREATMENT>='Saline'));
  VAR <TREATMENT> <BASELINE> <PARAMETER>;
RUN;
```

where PARAMETER has 5 levels and refers to the corneal fluorescein staining score for each region (inferior, superior, central, temporal, and nasal).

10.4.4 Multiplicity Consideration

To control for inflation of type 1 error rate due to multiple hypotheses, the analysis of the two primary endpoints will be conducted in a hierarchical manner.

If both primary endpoints demonstrate statistically significant superiority of NOV03 versus saline at the two-sided alpha = 0.05 level, the following secondary endpoints will be tested hierarchically to maintain an overall two-sided alpha = 0.05.

1. CFB of Dryness Score (VAS) at Day 15
2. CFB in total Corneal Fluorescein Staining (tCFS) (NEI scale) at Day 15
3. CFB of VAS burning/stinging at Day 57
4. CFB in central Corneal Fluorescein Staining (cCFS) (NEI scale) at Day 57

10.4.5 Primary Efficacy Analyses

The primary comparisons in this trial will be between NOV03 versus saline at Day 57 in the FAS with available data per subject using the following estimands:

- Population: Subjects with DED defined through enrollment criteria
- Endpoint:
 - CFB in tCFS in the study eye at Day 57
 - CFB of Dryness Score (VAS) at Day 57
- Intercurrent event:
 - Discontinuation of study medications is ignored. [treatment policy strategy]
 - Non-optimal compliance is ignored. [treatment policy strategy]

- Withdrawal due to any reason. Missing data not imputed. [hypothetical strategy]
- Population-level summary:
 - Difference in the mean CFB in tCFS in the study eye at Day 57 between NOV03 and saline.
 - Difference in the mean CFB of Dryness Score (VAS) at Day 57 between NOV03 and saline.

If the overall study discontinuation rate is $\geq 5\%$ then the primary analysis will be based on imputation methodology using the following estimands and the available data analyses will become robustness analyses.:

- Population: Subjects with DED defined through enrollment criteria
- Endpoint:
 - CFB in tCFS in the study eye at Day 57
 - CFB of Dryness Score (VAS) at Day 57
- Intercurrent event:
 - Discontinuation of study medications is ignored. [treatment policy strategy]
 - Non-optimal compliance is ignored. [treatment policy strategy]
 - Withdrawal due to lack of efficacy or adverse events. Baseline observation carried forward (BOCF) is used to impute missing data [hypothetical strategy].
 - Missing data without withdrawal or withdrawal due to reasons other than lack of efficacy or adverse events. Multiple imputations using randomized treatment-based Markov Chain Monte Carlo is used to impute missing data [hypothetical strategy].
- Population-level summary:
 - Difference in the mean CFB in tCFS in the study eye at Day 57 between NOV03 and saline.
 - Difference in the mean CFB in Dryness Score (VAS) at Day 57 between NOV03 and saline.

The primary comparison in this trial will be between NOV03 versus saline at Day 57. The primary efficacy endpoints (e.g. CFB in total corneal fluorescein staining [NEI scale] and Dryness Score) will be tested using hierarchical fixed sequence testing and summarized descriptively (n, mean, standard deviation, median, min, and max) and analyzed separately using an ANCOVA model with terms for baseline value, and treatment.

Least squares mean for each treatment group and for the difference between treatment groups will be presented from each model together with two-sided p-values (used for primary inference) and 95% confidence intervals.

Two-sample t-tests, Wilcoxon rank sum tests and mixed-effect repeated measures analysis comparing treatment groups will be performed as sensitivity analyses. The mixed-effect repeated measures model will include treatment, baseline value, visit, and the interaction between treatment and visit as fixed effects, and subject as a random effect. An unstructured

covariance matrix will initially be used to model the covariance among repeated measures; however, if the model fails to converge using this covariance structure, either heterogeneous TOEPLITZ, homogeneous TOEPLITZ, or compound symmetry will be implemented according to the Akaike information criterion with a correction for finite sample sizes (AICc).

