10.4.6 Secondary Efficacy Analyses

The following secondary endpoints will be tested hierarchically:

1. CFB of Dryness Score (VAS) at Day 15.
2. CFB in tCFS (NEI scale) at Day 15.
3. CFB VAS burning/stinging at Day 57.
4. CFB in central Corneal Fluorescein Staining (cCFS) (NEI scale) at Day 57.

Inference will only be made on these endpoints, at a 2-sided alpha = 0.05, if both primary endpoints and any higher order secondary endpoints are statistically significant at a 2-sided alpha = 0.05 in favor of NOV03.

Quantitative secondary efficacy endpoints will be summarized similarly to the primary efficacy endpoints.

The primary analysis of the secondary endpoints will use the FAS with available data per subject, assuming the overall study discontinuation rate is <5%. If the overall study discontinuation rate is $\geq 5\%$, then the primary analysis of the secondary endpoints will be based on imputation methodology as defined in [Section 10.4.5](#) and the available data analyses will become robustness analyses.

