6.5.7.3 Primary Efficacy Analyses

The primary comparisons in this trial will be between NOV03 versus saline at Day 57 in the FAS with available data per subject using the following estimands

- Endpoint:
 - CFB in tCFS in the study eye at Day 57
 - CFB of Dryness Score (VAS) at Day 57
- Intercurrent event:
 - Discontinuation of study medications is ignored. [treatment policy strategy]
 - Non-optimal compliance is ignored. [treatment policy strategy]
 - Withdrawal due to any reason. Missing data not imputed. [hypothetical strategy if overall study discontinuation rate is <5%]
- Population-level summary:
 - Difference in the mean CFB in tCFS in the study eye at Day 57 between NOV03 and saline
 - Difference in the mean CFB of Dryness Score (VAS) at Day 57 between NOV03 and saline

If the overall study discontinuation rate in the FAS is $\geq 5\%$ then the primary analysis will be based on imputation methodology using the following estimands:

- Endpoint:
 - CFB in tCFS in the study eye at Day 57
 - CFB of Dryness Score (VAS scale) at Day 57
- Intercurrent event:
 - Discontinuation of study medications is ignored. [treatment policy strategy]
 - Non-optimal compliance is ignored. [treatment policy strategy]
 - Withdrawal due to lack of efficacy or adverse events: baseline observation carried forward (BOCF) is used to impute missing data [hypothetical strategy if overall study discontinuation rate $\geq 5\%$]
 - Missing data without withdrawal or withdrawal due to reasons other than lack of efficacy or adverse events: multiple imputations using randomized treatment-based Markov Chain Monte Carlo (MCMC) is used to impute missing data [hypothetical strategy if overall study discontinuation rate $\geq 5\%$]
- Population-level summary:
 - Difference in the mean CFB in tCFS in the study eye at Day 57 between NOV03 and saline
 - Difference in the mean CFB of Dryness Score (VAS scale) at Day 57 between NOV03 and saline

The primary comparison in this trial will be between NOV03 versus saline at Day 57. The primary efficacy endpoints (e.g. CFB in total corneal fluorescein staining [NEI scale] and Dryness Score) will be tested using hierarchical fixed sequence testing and summarized descriptively (n, mean, standard deviation, median, min, and max) and analyzed separately using an ANCOVA model with terms for baseline value, and treatment.

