Least squares mean for each treatment group and for the difference between treatment groups will be presented from each model together with two-sided p-values (used for primary inference) and 95% confidence intervals.

Sample SAS ANCOVA code:

```
PROC GLM DATA=INDATA;
  CLASS <TREATMENT>;
  MODEL <ENDPOINT>=<TREATMENT> <BASELINE>;
  LSMEANS <TREATMENT> / CL ALPHA=0.05;
  LSMEANS <TREATMENT> / PDIFF CL ALPHA=0.05;
RUN;
```

Additional robustness analyses will include repeating the primary analysis on the PPS; the FAS imputing missing data using last observation carried forward (LOCF); the FAS imputing missing data using MCMC multiple imputation methodology under different assumptions of missingness (at random and not at random) each using 30 imputed values.

Sample SAS MCMC MI (missing at random):

```
PROC MI DATA=INDATA SEED=97656 OUT=OUTDATA MINIMUM=0 MAXIMUM=3 ROUND=1
NIMPUTE=30;
  MCMC INITIAL=EM;
  BY <TREATMENT>;
  VAR <BASELINE> <PARAMETER>;
RUN;
```

Where <PARAMETER> has 5 levels and refers to the CFS for each region (inferior, superior, central, temporal, and nasal).

Sample SAS MCMC MI (not missing at random):

```
PROC MI DATA=INDATA SEED=36797 OUT=MDATA MINIMUM=0 MAXIMUM=3 ROUND=1
NIMPUTE=30;
```

```
  MCMC IMPUTE=MONOTONE;
  VAR <BASELINE> <PARAMETER>;
RUN;
```

```
PROC MI DATA=MDATA SEED=38549 OUT=OUTDATA2 MINIMUM=. 0 0 MAXIMUM=. 3 3
ROUND=. 1 1;
  CLASS <TREATMENT>;
  MONOTONE REG(<PARAMETER>=<BASELINE> / DETAILS);
  MNAR MODEL(<PARAMETER> / MODELOBs=(<TREATMENT>='Saline'));
  VAR <TREATMENT> <BASELINE> <PARAMETER>;
RUN;
```

Where <PARAMETER> has 5 levels and refers to the CFS for each region (inferior, superior, central, temporal, and nasal).

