6.5.8.6.1 Imputation Method for Efficacy Endpoints

The primary analysis will be completed on the FAS with available data per subject, assuming the overall study discontinuation rate is $<5\%$. If the overall study discontinuation rate is $\geq 5\%$ then the primary analysis will be based on the primary imputation methodology as defined Section 6.5.7.3 and the available data analyses will become robustness analyses.

Additionally, robustness analyses will include repeating the primary analysis on the per protocol set (PPS); the FAS imputing missing data using last observation carried forward (LOCF); the FAS imputing missing data using Markov Chain Monte Carlo (MCMC) multiple

imputation methodology under different assumptions of missingness (at random and not at random) each using 30 imputed values.

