7 INDEX OF PLANNED TABLES, FIGURES, AND LISTINGS

Tables

Number	Title
14.1.1.1	Overall Disposition and Subject Accountability – FAS
14.1.1.2	Overall Disposition and Subject Accountability – PPS
14.1.1.3	Overall Disposition and Subject Accountability – SAF
14.1.2.1	Overview of Analysis Sets – Randomized Subjects
14.1.2.2	Reasons for Exclusion from Study Populations – Randomized Subjects
14.1.3	Major Protocol Deviations – FAS
14.1.4.1	Demographic and Baseline Characteristics – FAS
14.1.4.2	Demographic and Baseline Characteristics – PPS
14.1.4.3	Demographic and Baseline Characteristics – SAF
14.1.5.1	Baseline Ocular Characteristics – FAS
14.1.5.2	Baseline Ocular Characteristics – PPS
14.1.5.3	Baseline Ocular Characteristics – SAF
14.1.6.1	Study Eye Ocular Medical History – FAS
14.1.6.2	Fellow Eye Ocular Medical History – FAS
14.1.6.3	Subject Level Ocular Medical History – FAS
14.1.6.4	Non-ocular Medical History – FAS

- 14.1.7.1 Study Eye Ocular Concomitant Medications – FAS
- 14.1.7.2 Fellow Eye Ocular Concomitant Medications – FAS
- 14.1.7.3 Subject Level Ocular Concomitant Medications – FAS
- 14.1.7.4 Non-ocular Concomitant Medications – FAS
- 14.1.8 Study Medication Exposure and Compliance – SAF
- 14.2.1.1 Analyses of Change from Baseline tCFS and Dryness Score (VAS) at Day 57 – FAS
- 14.2.1.2 Analyses of Change from Baseline tCFS and Dryness Score (VAS) at Day 57 – PPS
- 14.2.2 Robustness Analyses of Change from Baseline tCFS and Dryness Score (VAS) at Day 57 (Discontinuation Rate $\geq 5\%$) – FAS
- 14.2.3 Sensitivity Analyses of Change from Baseline tCFS and Dryness Score (VAS) at Day 57 – FAS
- 14.2.4.1 Analyses of Secondary Efficacy Endpoints – FAS
- 14.2.4.2 Sensitivity Analyses of Secondary Efficacy Endpoints – FAS
- 14.2.5.1 Analysis of Dryness Score (VAS) – FAS
- 14.2.5.2 Sensitivity Analysis of Dryness Score (VAS) – FAS
- 14.2.6.1 Analysis of Study Eye tCFS – FAS
- 14.2.6.2 Analysis of Fellow Eye tCFS – FAS
- 14.2.6.3 Sensitivity Analysis of Study Eye tCFS – FAS
- 14.2.6.4 Sensitivity Analysis of Fellow Eye tCFS – FAS
- 14.2.7.1 Analysis of Study Eye Central Sub-region CFS (NEI scale) – FAS
- 14.2.7.2 Analysis of Fellow Eye Central Sub-region CFS (NEI scale) – FAS
- 14.2.7.3 Sensitivity Analysis of Study Eye Central Sub-region CFS (NEI scale) – FAS
- 14.2.7.4 Sensitivity Analysis of Fellow Eye Central Sub-region CFS (NEI scale) – FAS
- 14.2.7.5 Analysis of Study Eye Inferior Sub-region CFS (NEI scale) – FAS

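### If discontinuation reaches 5%, the only printed imputation model ignores the Day 15 and Day 29 scores and does not fit the VAS endpoints; an all-visit, endpoint-specific model is a cheap improvement

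*Protocol*

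**What the plan says.** Below 5% discontinuation, the primary analysis uses available data. At 5% or more, Protocol 10.4.5 and SAP 6.5.7.3 switch to imputation. Withdrawals for lack of efficacy or adverse events get BOCF. For everything else the Protocol says "Multiple imputations using randomized treatment-based Markov Chain Monte Carlo is used to impute missing data", and the SAP says the same: "multiple imputations using randomized treatment-based Markov Chain Monte Carlo (MCMC) is used to impute missing data". The secondary endpoints follow: in that case, "then the primary analysis of the secondary endpoints will be based on imputation methodology as defined in" Protocol 10.4.5.

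Neither section gives this primary imputation a variable list, limits, number of imputations or pooling rule. The cross-references lead back to the same place: SAP 6.5.8.6.1 relies on the "primary imputation methodology as defined Section 6.5.7.3".

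The only imputation code is in Protocol 10.4.3 and SAP 6.5.7.3, introduced under the robustness analyses with 30 imputations:

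- The SAP call under missing at random (MAR) opens "PROC MI DATA=INDATA SEED=97656 OUT=OUTDATA MINIMUM=0 MAXIMUM=3 ROUND=1", runs separately by treatment, and lists "VAR <BASELINE> <PARAMETER>".
- The Protocol states that the model is run visit by visit and explains the variable: "where PARAMETER has 5 levels and refers to the corneal fluorescein staining" score for each of five regions.

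**The concern.** Two things follow for the branch that the planning assumption makes likely.

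- **Interim visits.** The printed model predicts a missing Day 57 value from baseline only. A subject who left after Day 29 has Day 15 and Day 29 scores that say much more about Day 57, and the model does not use them. If leaving is related to those scores, missing at random given baseline fails, while missing at random given all visits may still hold.
- **VAS endpoints.** Limits of 0-3 with integer rounding belong to staining regions. Dryness Day 57 (second primary), Dryness Day 15 and burning/stinging Day 57 are all alpha-controlled, and no model is written for them. The same gap exists in the MAR and not-at-random robustness analyses, which repeat the primary analysis of both primary endpoints.

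At stake are a small, avoidable bias if dropout is informative, and a model for a primary endpoint that still has to be chosen.

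**Working it through.** **1. The plan's own figures (Protocol 10.3).** The inputs are 250 per arm, Dryness difference -10, SD 28, two-sided alpha 0.05.

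- SE = 28 x sqrt(2/250) = 2.504, and 10/2.504 = 3.993.
- Power = Phi(3.993 - 1.960) = 0.979. tCFS has the same ratio (1.0/2.8), so it also gives 0.979.
- Joint power = 0.979 x 0.979 = 0.958.
- 250/0.9 = 278, against 280 planned.

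All of these reproduce.

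**2. Chance of reaching the imputation branch.** 5% of 560 is 28 subjects. The binomial P(X >= 28 | 560, p) is:

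| True discontinuation | Probability |
|---|---|
| 10% (planned) | >0.9999 |
| 8% | 0.998 |
| 6% | 0.86 |
| 5% | 0.53 |
| 4% | 0.14 |

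**3. Do the printed limits suit a VAS score?** Dryness is stratified at 70 (Protocol 4.4) and has an assumed SD of 28. For an assumed mean of 35-55 and SD 28, an unbounded normal draw rounds to 0-3 with probability 2.8% (mean 35) to 0.9% (mean 55). The code was not written for VAS.

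**4. Size of the baseline-only bias for Dryness Day 57.** The documents give no correlations or dropout mechanism, so these are assumptions:

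- 10% missing per arm (28 of 280), half BOCF, so 5% (14 subjects) are handled by MI;
- correlation between post-baseline visits, rho, of 0.5 or 0.7;
- correlation of baseline with later visits, r, equal to rho, or 0 as an extreme;
- in one arm, dropout log-odds rise by 0.5 or 1.0 per SD of the Day 29 score. Leavers then differ from completers at Day 29 by d of about 0.49 or 0.91 SD.

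Of that shift, rho x d carries through to Day 57, and baseline recovers r x r x d. The bias is therefore approximately 0.05 x (rho - r^2) x d x 28:

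| rho | r | d | Bias (VAS points) |
|---|---|---|---|
| 0.5 | 0.5 | 0.49 | 0.05 x 0.25 x 0.49 x 28 = 0.17 |
| 0.5 | 0.5 | 0.91 | 0.05 x 0.25 x 0.91 x 28 = 0.32 |
| 0.7 | 0.7 | 0.49 | 0.05 x 0.21 x 0.49 x 28 = 0.14 |
| 0.7 | 0.7 | 0.91 | 0.05 x 0.21 x 0.91 x 28 = 0.27 |
| 0.7 | 0 | 0.91 | 0.05 x 0.70 x 0.91 x 28 = 0.89 |

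Large-sample simulation agrees (0.14-0.32 with r = rho, 0.88 in the last row). Imputing from baseline, Day 15 and Day 29 leaves essentially no bias, as expected when dropout is simulated on Day 29.

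**5. Finite-sample check.** This used 280 per arm, 30 imputations, Rubin's rules, and 28 taken as the ANCOVA residual SD. With r = rho the mean gap was 0.20-0.40, and with r = 0 it was 0.35-0.90. The SE was 2.42-2.48. Relative to 2.45, that is 0.20/2.45 = 0.08 to 0.40/2.45 = 0.16 SE, and at most 0.90/2.45 = 0.37 SE.

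**6. Equal dropout.** The mean gap was -0.01. The SE was 2.43-2.48 (baseline only) against 2.42-2.45 (all visits), a gain of about 1%. Within a single trial the two models still differed with an SD of 0.27-0.44 points.

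**7. Order of BOCF and MI.** Setting BOCF values before rather than after imputation moved the estimate by -0.03 to +0.11 points.

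**The case against.** The strongest reply is that the plan fixes more than it seems to. It names MCMC by randomized arm, says which withdrawals get BOCF and which get MI, and specifies the ANCOVA. The SAP labels its code as a sample. SAP Section 4 requires changes before lock and unmasking to be documented as an amendment, so a model could not be chosen silently. All of this stands.

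Baseline-only MI by arm is also a legitimate missing-at-random specification. The plan sends lack-of-efficacy and adverse-event withdrawals to BOCF, so response-related dropout is least expected among the subjects left for MI, although withdrawals by choice may carry some. The criticism chiefly concerns Day 57, because a subject who leaves before Day 15 has no interim score. A mixed model using all visits is already planned and could show a discrepancy, though only as a sensitivity analysis. These points limit the size of the problem but do not remove it.

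A reader might infer three stronger things that the documents do not support:

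- **That Dryness has no defined analysis.** Only the detail of its imputation model is missing.
- **That the 0-3 limits would be applied to VAS scores.** Simulated literally, with 7% of saline and 3% of NOV03 subjects imputed, that moved the Dryness estimate from -9.4 to -7.2 and power from 97% to 84%. Both documents tie the limits to staining regions, so this is not what the plan says.
- **That the table index proves imputed Dryness results are planned.** The title "Robustness Analyses of Change from Baseline tCFS and Dryness Score (VAS) at Day 57" is qualified by discontinuation of at least 5%. In that branch the available-data analyses are themselves robustness analyses. The text of SAP 6.5.7.3 and 6.5.8.6.1 is the better support.

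**Conclusion.** The point holds as a low-cost improvement. Under the planned 10% discontinuation, the imputation branch is almost certainly the primary analysis. Its only printed model leaves out collected Day 15 and Day 29 data and does not fit three of the six alpha-controlled endpoints.

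The gain from using all visits is real but small and conditional. It is about 0.15-0.4 VAS points when baseline predicts Day 57 as well as the visits predict each other. It is up to about 0.9 only at zero baseline correlation. Either figure requires MI-handled dropout to depend on interim response in one arm. The direction depends on the arm and on who leaves. With equal dropout there is no bias, and the plan's power statement is sound.

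These sizes measure the omission of interim visits. They do not measure the missing VAS specification, which is a gap in pre-specification with no bias attached. The unstated number of imputations, pooling and BOCF order are matters of clarity only.

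**What to change.** In Protocol 10.4.3 and 10.4.5 and SAP 6.5.7.3, write out the primary MI:

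- MCMC by randomized arm, with baseline, Day 15, Day 29 and Day 57 of the endpoint in the variable list.
- For Dryness and burning/stinging, use the VAS scale's own limits, without the 0-3 bounds or integer rounding. For staining regions, keep 0-3.
- Use the same endpoint-specific limits in the MAR and not-at-random robustness code.
- As clarification in the same edit, state 30 imputations, pooling by Rubin's rules, and that BOCF values are set after MI.

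Keep the BOCF rule and the mixed-model sensitivity analysis as planned. The cost is some wording, a few lines of code and a slightly larger imputation model. No new data are needed and the sample size does not change. The edit should be made before unmasking.
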